3.2 Exclusion Criteria

1. Involvement in the planning and/or conduct of the study (applies to both AstraZeneca staff and/or staff at the study site). Previous enrollment in the present study.
2. Participation in another clinical study with an investigational product for cancer during the last 12 months.
3. Any previous treatment with a PD1 or PD-L1 inhibitor, including durvalumab.
4. Symptomatic or uncontrolled brain metastases requiring concurrent treatment, inclusive of but not limited to surgery, radiation and/or corticosteroids, in excess of prednisone 10 mg/d or equivalent.
5. Sensitizing mutations in *EGFR* or rearrangements in *ALK* or *ROS1*.
6. History of allergic reactions attributed to compounds of similar chemical or biologic composition to durvalumab.
7. Current or prior use of immunosuppressive medication within 28 days before the first dose of durvalumab, with the exceptions of intranasal and inhaled corticosteroids. Patients may be on systemic corticosteroids provided the dose does not exceed prednisone 10 mg/d or equivalent for 1 week prior to study drug administration.

HCC #:16-054

Version Date: 008/11/2020

8. Active autoimmune disease requiring systemic treatment within the past 2 years.
NOTE: Subjects with autoimmune disease, such as vitiligo, Grave's disease, or psoriasis not requiring systemic treatment (within the past 2 years) are not excluded.
9. Active or prior documented inflammatory bowel disease (e.g., Crohn's disease, ulcerative colitis).
10. History of primary immunodeficiency.
11. History of allogeneic organ transplant.
12. Uncontrolled intercurrent illness including, but not limited to, ongoing or active infection, symptomatic congestive heart failure, uncontrolled hypertension, unstable angina pectoris, cardiac arrhythmia, active peptic ulcer disease or gastritis, active bleeding diatheses including any subject known to have evidence of acute or chronic hepatitis B, hepatitis C or human immunodeficiency virus (HIV), or psychiatric illness/social situations that would limit compliance with study requirements or compromise the ability of the subject to give written informed consent.
13. Known history of previous clinical diagnosis of tuberculosis.
14. History of leptomeningeal carcinomatosis.
15. Receipt of live attenuated vaccination within 30 days prior to study entry or within 30 days of receiving durvalumab.

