6.2 General Concomitant Medication and Supportive Care Guidelines

HCC #:16-054

Version Date: 008/11/2020

Investigators may prescribe concomitant medications or treatments (e.g., acetaminophen, diphenhydramine) deemed necessary to provide adequate prophylactic or supportive care except for those medications identified as “excluded” as listed below.

Excluded Concomitant Medications

The following medications are considered exclusionary during the study.

1. Any investigational anticancer therapy other than the protocol specified therapy.
2. Any concurrent chemotherapy, radiotherapy (except palliative radiotherapy), immunotherapy, biologic or hormonal therapy for cancer treatment. Concurrent use of hormones for non-cancer related conditions (e.g., insulin for diabetes and hormone replacement therapy) is acceptable. NOTE: Local treatment of isolated lesions for palliative intent is acceptable (e.g., by local surgery or radiotherapy).
3. Immunosuppressive medications including, but not limited to systemic corticosteroids at doses not exceeding 10 mg/day of prednisone or equivalent, methotrexate, azathioprine, and TNF- α blockers. Use of immunosuppressive medications for the management of investigational product-related AEs or in subjects with contrast allergies is acceptable. In addition, use of inhaled and intranasal corticosteroids is permitted. A temporary period of steroids will be allowed for different indications, at the discretion of the principal investigator (e.g., chronic obstructive pulmonary disease, radiation, nausea, etc).
4. Live attenuated vaccines within 30 days of durvalumab dosing (ie, 30 days prior to the first dose, during treatment with durvalumab and for 30 days post discontinuation of durvalumab. Inactivated vaccines, such as the injectable influenza vaccine, are permitted.

Rescue Medications	
Rescue/supportive medication/class of drug:	Usage:
Concomitant medications or treatments (eg, acetaminophen or diphenhydramine) deemed necessary by the Investigator to provide adequate prophylactic or supportive care, except for those medications identified as “prohibited” as listed above	To be administered as prescribed by the Investigator
Best supportive care (including antibiotics, nutritional support, growth factor support, correction of metabolic disorders, optimal symptom control, and pain management [including palliative radiotherapy, etc])	Should be used when necessary for all patients

Contraception

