APPENDIX D: DOSING DELAYS/DOSE MODIFICATIONS

Table 1- Immune-Mediated Reactions				
	Dose Modifications		Toxicity Management	
Immune-related Adverse Events (Overall Management For toxicities not noted below)	
Drug administration modifications of study drug/study regimen will be made to manage potential immune-related AEs based on severity of treatment-emergent toxicities graded per NCI CTCAE v4.03.
 
In addition to the criteria for permanent discontinuation of study drug/regimen based on CTC grade/severity (table below), permanently discontinue study drug/study regimen for the following conditions:
 
 • Inability to reduce corticosteroid to a dose of ≤ 10 mg of prednisone per day (or equivalent) within 12 weeks after last dose of study drug/regimen • Recurrence of a previously experienced Grade 3 treatment-related AE following resumption of dosing. 		
It is recommended that management of irAEs follow the guidelines presented in this table:
 
 - Patients should be thoroughly evaluated to rule out any alternative etiology (e.g., disease progression, concomitant medications, infections, etc.) - In the absence of a clear alternative etiology, all events should be considered potentially immune related. - Symptomatic and topical therapy should be considered for low-grade (Grade 1 or 2, unless otherwise specified) events - For persistent (greater than 3 to 5 days) low-grade (Grade 2) or severe (Grade ≥ 3) events promptly start prednisone PO 1-2mg/kg/day or IV equivalent - If symptoms recur or worsen during corticosteroid tapering (28 days of taper), increase the corticosteroid dose (prednisone dose [e.g. up to 2-4mg/kg/day PO or IV equivalent]) until stabilization or improvement of symptoms, then resume corticosteroid tapering at a slower rate (> 28 days of taper) - More potent immunosuppressives such as TNF inhibitors (e.g. infliximab) – (also refer to the individual sections of the immune related adverse event for specific type of immunosuppressive) should be considered for events not responding to systemic steroids. - Discontinuation of study drug is not mandated for Grade 3 / Grade 4 inflammatory reactions attributed to local tumour response (e.g. inflammatory reaction at sites of metastatic disease, lymph nodes etc.). Continuation of study drug in this 	
	Grade 1	No dose modification		

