	Grade 2 (Depending on the type of endocrinopathy, refer to NCI CTCAE version 4.03 for defining the CTC grade/severity 2)	
For Grade 2 endocrinopathy other than hypothyroidism, hold study drug/study regimen dose until subject is clinically stable
 
•If toxicity worsens then treat as Grade 3 or Grade 4
 
Study drug/study regimen can be resumed once
	
For Grade 2: (including those with symptomatic endocrinopathy)
 
 - Isolated hypothyroidism may be treated with replacement therapy without treatment interruption and without corticosteroids - Initiate hormone replacement as needed for management - Evaluate endocrine function, and as clinically indicated, consider pituitary scan - For patients with abnormal endocrine work up, except for those with isolated hypothyroidism, consider short-term, corticosteroids (e.g., 1-2mg/kg/day methylprednisolone or IV equivalent) and prompt initiation of treatment with relevant hormone replacement (e.g. Levothyroxine, hydrocortisone, or sex hormones). - - Once improving, gradually taper steroids over ≥28 days and consider prophylactic antibiotics, antifungals and anti PCP

Table 1- Immune-Mediated Reactions (continued)			
		Dose Modifications	Toxicity Management
		
event stabilizes and after completion of steroid taper.
 
Patients with endocrinopathies who may require prolonged or continued steroid replacement can be retreated with study drug/study regimen on the following conditions: 1) the event stabilizes and is controlled, 2) the patient is clinically stable as per Investigator or treating physician's clinical judgement, and 3) doses of prednisone are at less than or equal to 10mg/day or equivalent.
	
treatment (please refer to current NCCN guidelines for treatment of cancer-related infections [Category 2B recommendation])
 
 - For patients with normal endocrine work up (lab or MRI scans), repeat labs/MRI as clinically indicated.

Table 1- Immune-Mediated Reactions (continued)			
		Dose Modifications	Toxicity Management

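### Section 6.2 item 3 bans systemic steroids at or below 10 mg/day prednisone, the dose range that the entry criteria and Appendix D allow

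*Combined protocol and SAP*

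**What the plan says.** Section 6.2 opens its list of excluded concomitant medications with "The following medications are considered exclusionary during the study". Item 3 covers immunosuppressive drugs and gives as its first example "systemic corticosteroids at doses not exceeding 10 mg/day of prednisone or equivalent", alongside methotrexate, azathioprine and TNF-α blockers.

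The same item then sets out exceptions. One reads "Use of immunosuppressive medications for the management of investigational product-related AEs or in subjects with contrast allergies is acceptable". Inhaled and intranasal steroids are also allowed, as is a temporary course for other indications at the principal investigator's discretion. Item 2 separately allows hormones for conditions other than cancer, including replacement therapy.

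The entry criteria in Section 3.2 put the limit the other way round. Criterion 7 lets patients be on "systemic corticosteroids provided the dose does not exceed prednisone 10 mg/d or equivalent for 1 week prior to study drug administration". Criterion 4, on brain metastases that need treatment, refers to "surgery, radiation and/or corticosteroids, in excess of prednisone 10 mg/d or equivalent".

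Appendix D, Table 1 uses the same limit for managing immune-related events. It requires permanent discontinuation for "Inability to reduce corticosteroid to a dose of ≤ 10 mg of prednisone per day (or equivalent) within 12 weeks" of the last dose. It allows retreatment of patients with endocrinopathies who need prolonged steroid replacement, on conditions that include "doses of prednisone are at less than or equal to 10mg/day or equivalent".

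**The concern.** A patient on a stable dose of 10 mg/day or less can be enrolled correctly and, once on study, be taking a drug that item 3 names as excluded. The protocol gives no reason for such a switch and describes no taper.

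This is a rule that sites have to apply. The study calendar in Section 11 has concomitant medications reviewed at all visits. Section 13.1 puts protocol deviations before a monthly review, and Section 13.2 provides for independent compliance monitoring at least once a year. A site that follows item 3 to the letter would either record a deviation for an eligible patient or stop a steroid that the entry criteria permit. Two sites, or a site and a monitor, could read the line in opposite ways.

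**Working it through.** No arithmetic beyond a count applies. The check sets every statement of the 10 mg/day prednisone limit side by side.

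| Place | What it governs | Status of 10 mg/day or less |
|---|---|---|
| Section 3.2, criterion 4 | Brain metastases at entry | Not restricted; the restriction starts above 10 mg/day |
| Section 3.2, criterion 7 | Steroid use in the week before study drug | Permitted |
| Section 6.2, item 3 | Concomitant medication on study | **Named as excluded** |
| Appendix D, Table 1, overall management | Permanent discontinuation | Acceptable; stop only if this level cannot be reached |
| Appendix D, Table 1, overall management, Grade 2 | Retreatment with endocrinopathy | Permitted while on durvalumab |
| Appendix D, Table 1, endocrinopathy, Grade 2 | Retreatment with endocrinopathy | Permitted while on durvalumab |

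Count: 2 (Section 3.2) + 1 (Section 6.2) + 3 (Appendix D) = 6 statements. Those that treat 10 mg/day as a permitted ceiling: 2 + 3 = 5. Those that reverse it: 1.

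**Does the literal text permit high doses?** No. Item 3 introduces its examples as a non-exhaustive list, so doses above 10 mg/day stay within the general ban on immunosuppressives. The error is that the low dose is named as banned; the high dose is not released.

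**Does Appendix D conflict with item 3?** No. Steroids given for drug-related events fall under item 3's own exception. Appendix D shows what was intended, and no more than that.

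**Who is left in conflict?** Take the patients whom criterion 7 admits on low-dose systemic steroids and remove everyone covered by an exception: drug-related events, contrast allergy, temporary use at the principal investigator's discretion, and hormone replacement under item 2. What remains is stable, continuing prednisone at 10 mg/day or less for some other reason. Continuing use is not temporary, so the discretionary exception does not reach it.

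**Does any analysis change?** No. Section 14.2 defines the safety cohort by receipt of study drug, and the possible exclusions from the efficacy cohort by early withdrawal for reasons unrelated to progression or toxicity. Neither depends on concomitant steroids or on recorded deviations. The sample size in Section 14.1 does not use this rule.

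**The case against.** The strongest reply is that the error is small and errs on the safe side. High doses stay excluded, so nobody is exposed to more immunosuppression than intended. Only criterion 7 truly collides with item 3: criterion 4 is about brain metastases, Appendix D falls under an exception, and two of its three statements repeat each other. Even criterion 7 speaks of the week before study drug while item 3 speaks of the study period, so the two cover adjacent periods. The exceptions remove most steroid use. A sensible reader with the whole protocol would take *not* for a slip, and the protocol nowhere says that staff would stop a permitted steroid.

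Much of this stands as a limit on size. The operative clash is criterion 7 against item 3, the five-to-one count is evidence of intent and not of impact, and the harm at sites is a possibility that the documents do not quantify. It does not rescue the wording. Adjacent periods meet at the first infusion, where the same dose changes from allowed to excluded without explanation. Relying on the principal investigator's discretion would mean a case-by-case waiver for something the entry criteria already allow.

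It can also be said that removing one word leaves low doses caught by the non-exhaustive list. Read together with criterion 7, a stated threshold of more than 10 mg/day naturally leaves lower doses permitted. An explicit sentence would help but is not essential.

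**Conclusion.** The concern holds: item 3 is wrong as written and contradicts exclusion criterion 7. It is a drafting error in an operative dose threshold. Its reach is limited to patients on continuing low-dose systemic steroids outside the stated exceptions. How many there will be cannot be derived from the documents, which give no rate of such use; zero is possible. The consequences are for site conduct, patient care at the margin and the classification of deviations. No planned analysis, cohort or sample size figure changes. The conclusion assumes that 10 mg/day was meant as a permitted ceiling throughout, which the other five statements support and nothing in the documents contradicts. The correction should be made.

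**What to change.** In Section 6.2 item 3, delete *not*, so that the excluded example becomes systemic corticosteroids at doses exceeding 10 mg/day of prednisone or equivalent. Keep the existing exceptions as they stand. If the item is being reissued anyway, a short added sentence stating that 10 mg/day or less is permitted would remove any residual doubt.

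The cost is a one-line wording correction. Eligibility, dosing, data collection and analysis stay as they are.

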6.3 Patient Reported Outcomes for FACT-L

To ensure completion of the FACT-L questionnaires at the appropriate time-points, assigned research staff must adhere to the instructions in this section. The patient should complete the FACT-L questionnaires in clinic at the following times: at baseline, prior to the start of each cycle, and at the end of therapy.

Research staff should instruct the patient how to properly fill in the FACT-L questionnaire per the following instructions:

HCC #:16-054

Version Date: 008/11/2020

- All questionnaires must be completed prior to any other study procedures (baseline following informed consent) and before discussion of current disease status to avoid biasing the patient's responses to the questions.
- Provide a private environment for the patient to answer the questions.
- Provide sufficient time for the patient to complete the questionnaire at their own pace.
- Avoid assistance from relatives, friends or clinic staff to help the patient answer the questionnaires. However, if the patient is unable to read the questionnaire (due to vision impairment such as blindness or uncorrected vision, illiteracy), the questionnaires may be read out loud by trained clinic staff and responses recorded.
- When the patient completes the questionnaire, it should be handed back to the person responsible for the questionnaires, checking for completeness prior to initiating any other procedures.
- Only one answer should be recorded for each question.

6.4 Duration of Therapy

Treatment may continue for up to 12 months (maximum 12 doses) or until one of the criteria for durvalumab discontinuation is met.

Permanent discontinuation of durvalumab

An individual subject will not receive any further investigational product if any of the following occur in the subject in question:

- Confirmation of PD and investigator determination that the subject is no longer benefiting from treatment with durvalumab
- Withdrawal of consent or lost to follow-up
- Adverse event that, in the opinion of the investigator or the sponsor, contraindicates further dosing
- Subject is determined to have met one or more of the exclusion criteria for study participation at study entry and continuing investigational therapy might constitute a safety risk
- Pregnancy or intent to become pregnant
- Any AE that meets criteria for discontinuation as defined in Appendix D.
- Grade \geq 3 infusion reaction
- Subject noncompliance that, in the opinion of the investigator or sponsor, warrants withdrawal; eg, refusal to adhere to scheduled visits

HCC #:16-054

Version Date: 008/11/2020

- Initiation of alternative anticancer therapy including another investigational agent

Subjects who are permanently discontinued from further receipt of investigational product, regardless of the reason (withdrawal of consent, due to an AE, other), will be identified as having permanently discontinued treatment.

Subjects who are permanently discontinued from receiving investigational product will be followed for safety per Appendix E or F, unless consent is withdrawn or the subject is lost to follow-up or enrolled in another clinical study. All subjects will be followed for survival. Subjects who decline to return to the site for evaluations will be offered follow-up by phone at months 2, 3, 4, 6, 8, 10, 12 after stopping treatment, and then every 2 months after that as an alternative.

Withdrawal of consent

If consent is withdrawn, the subject will not receive any further investigational product or further study observation.

6.5 Duration of Follow Up

Patients will be followed for 12 months after discontinuation of study therapy or until death, whichever occurs first. Patients discontinuing study therapy for unacceptable adverse event(s) will be followed at least until resolution or stabilization of the adverse event (Appendix E).

At the discretion of the sponsor-investigator (or sponsor/investigator) the study may be closed prematurely.

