8.3.3 Reporting of deaths

All deaths that occur during the study or within the protocol-defined 90-day post-last dose of durvalumab safety follow-up period must be reported as follows:

Death that is clearly the result of disease progression should be documented but should not be reported as an SAE.

Where death is not due (or not clearly due) to progression of the disease under study, the AE causing the death must be reported to as a SAE within **24 hours** (see Section 8.3.2 for further details). The report should contain a comment regarding the co-involvement of progression of disease, if appropriate, and should assign main and contributory causes of death.

Deaths with an unknown cause should always be reported as a SAE.

Deaths that occur following the protocol-defined 90-day post-last-dose of durvalumab safety follow-up period will be documented as events for survival analysis, but will not be reported as an SAE.

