APPENDIX E								
Schedule of study procedures: follow-up for subjects who have completed durvalumab treatment and achieved disease control (until confirmed progression of disease) and subjects who have discontinued durvalumab due to toxicity in the absence of confirmed progression of disease								
Evaluation	Time Since Last Dose of durvalumab							
	Day (± 3)	Months (± 1 week)						12 Months, then Every 6 Months thereafter (± 2 weeks)
	30	2	3	4	6	8	10	
Physical examination ^a	X							
Vital signs (temperature, respiratory rate, blood pressure, pulse)	Per institutional standard of care or as clinically indicated							
Weight	X							
Serum β hCG	X							
AE/SAE assessment	X	X	X					
Concomitant medications	X	X	X					
Palliative radiotherapy	As clinically indicated \longrightarrow							
ECOG performance status	X	X	X		X (and month 9)			X
Subsequent anti-cancer therapy	X	X	X	X	X	X	X	X
Survival status: phone contact with subjects who refuse to return for evaluations and agree to be contacted		X	X	X	X	X	X	X (every 2 months)
Hematology	X	X	X					X
Serum chemistry	X	X	X					
Thyroid function tests (TSH, and fT3 and fT4) ^b	X							
FACT-L questionnaire	X			X	
For subjects who achieve disease control following 12 months of treatment, patient questionnaires should be completed every 12 weeks relative to the date of enrollment until confirmed PD by RECIST 1.1 by investigational site review.
 
For subjects who discontinue study drug due to toxicity or a reason other than confirmed PD, patient questionnaires should be completed relative to the date of enrollment as follows: every 8 weeks for the first 12 months, then every 12 weeks until confirmed PD by RECIST 1.1 by investigational site review.
			

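### Section 6.5 stops follow-up 12 months after therapy ends, while 6.4 and Appendices E/F continue it for survival; if 6.5 is followed, OS censoring depends on treatment duration and the OS curve beyond month 12 may be biased upward.

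*Combined protocol and SAP*

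**What the plan says.** Section 6.5 sets one limit for all patients: "Patients will be followed for 12 months after discontinuation of study therapy or until death, whichever occurs first". Naming death as the other endpoint means the sentence covers survival, not only safety.

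Section 6.4 sets no such limit. It says "All subjects will be followed for survival". Patients who decline clinic visits are offered phone contact "at months 2, 3, 4, 6, 8, 10, 12 after stopping treatment, and then every 2 months after that". In Appendices E and F the last column is headed "12 Months, then Every 6 Months thereafter", and the survival-status row in that column specifies contact every 2 months. Section 8.3.3 says that deaths after the 90-day safety window "will be documented as events for survival analysis", again with no end date.

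Section 14.3 makes the Kaplan-Meier OS curve, the median and its 90% confidence interval a primary analysis. It does not say when a living patient is censored. Section 6.4 allows at most 12 doses over 12 months, and one listed reason for stopping is "Confirmation of PD and investigator determination that the subject is no longer benefiting from treatment with durvalumab".

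**The concern.** Kaplan-Meier estimation requires that a patient censored at time t has the same later risk as those still under observation at t. Under 6.5 the censoring time is treatment duration plus 12 months. A patient who stops at month 2 and is still alive leaves the risk set at month 14. A patient treated for the full course stays until about month 22. Since progression is a main reason for stopping, survivors with the worse outlook would leave first, and the late curve would lean on those who did well.

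That matters because the OS curve is a primary result, section 14.3 interprets it alongside durable responses, and section 14.1 expects such responses in a minority. Median OS by PD-L1 status is a secondary objective. A subgroup median above 12 months would fall in the affected range.

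**Working it through.** **1. The plan's own power figure.** Inputs from 14.1 and 14.3: N = 50, medians of 9 and 5 months, at least 6 months of follow-up, and Greenwood variance on log survival. Everyone is observed to month 5. The lower confidence limit for the median therefore exceeds 5 months when S·exp(−z·√((1−S)/(50·S))) > 0.5, where S is the observed proportion alive at month 5.

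- 90% interval (z = 1.645): 19 deaths give S = 0.62 and a limit of 0.517; 20 deaths give 0.496. The cut-off is 19 deaths.
- 95% interval (z = 1.960): 18 deaths give 0.520; 19 give 0.499. The cut-off is 18 deaths.
- With an exponential median of 9 months, the probability of death by month 5 is 1 − 2^(−5/9) = 0.320. The binomial probability of at most 19 deaths in 50 is 85.7%, and of at most 18 is 78.0%.

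The stated 85% and 78% are reproduced. They depend only on survival to month 5.

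**2. When 6.5 can censor.** The earliest time is just over 12 months. For the latest, 12 doses every 4 weeks put the last at week (12 − 1) × 4 = 44, or 44 × 7 / 30.44 = 10.1 months. Adding 12 gives about month 22. Counted from the last dose, nobody is at risk after that, so no estimate beyond month 22 is used here.

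**3. Size of the bias.** The documents give no progression-free survival or post-progression hazard for this population, so these are assumed. Each model is calibrated to S(9) = 0.5. Large simulated cohorts are censored at stopping time plus 12 months, and Kaplan-Meier is compared with true survival.

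*No durable group.* Median time to progression is 3-6 months, treatment stops at progression, and the hazard of death is then multiplied by k.

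*Durable group.* A fraction f has median OS of 24 or 36 months and completes treatment. The rest have median OS m and stop with a median of 2 months. Calibration for f = 0.2 and 24 months: 0.2 × 2^(−9/24) + 0.8 × 2^(−9/m) = 0.5 gives m = 7.44. True S(18) is then 0.2 × 0.595 + 0.8 × 0.187 = 0.268.

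| Model | S(18) true / KM | S(21) true / KM |
|---|---|---|
| Progression 4 months, k = 1 | 0.250 / 0.251 | 0.198 / 0.198 |
| Progression 4 months, k = 4 | 0.181 / 0.187 | 0.126 / 0.135 |
| Progression 4 months, k = 8 | 0.167 / 0.174 | 0.112 / 0.122 |
| 20% durable, 24 months | 0.268 / 0.294 | 0.222 / 0.265 |
| 20% durable, 36 months | 0.279 / 0.310 | 0.236 / 0.289 |
| 40% durable, 24 months | 0.299 / 0.322 | 0.260 / 0.294 |

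The k = 1 row shows no bias; its 0.001 difference is simulation error. Without a durable group the excess is at most 0.7 points at 18 months and 1.0 at 21. With 20-40% durable it is 2.3 to 3.1 points at 18 months and 3.4 to 5.3 at 21, if the others stop with a median of 2 months. In a further model with 20% durable, the 18-month excess falls from 2.8 points to 1.8 or 1.2 when stopping lags progression by 1 or 2 months. It is 0.5 or less when median progression-free survival is 4 months. In every model the difference at month 12 and earlier is zero.

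**4. Effect on the decision rule.** In 5,000 simulated trials of 50 patients (progression 4 months, k = 4), run with and without the planned administrative censoring, the 6.5 rule never changed the lower 90% limit. The median was unchanged in more than 99.5%. The probabilities of a lower limit above 5 months and of a median of at least 9 months did not change. The upper limit changed in 11-16% of trials.

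**The case against.** The strongest reply is that the more specific text already avoids the problem. Section 6.4, the appendices and 8.3.3 all continue survival follow-up, and 14.3 nowhere tells the analyst to censor at the 6.5 limit. If sites follow 6.4, the bias is zero. This stands, and it is why the bias is stated conditionally. It does not remove the contradiction, because staff who follow 6.5 would stop contact at month 12 off treatment.

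The second reply is that the affected region is thin. With 18 months of accrual, 6 months of follow-up and an exponential median of 9 months, the expected number at risk at month 18 is 50 × 0.25 × 6/18 = 4.2, and at month 21 it is 50 × 0.198 × 3/18 = 1.7. Even with all 50 patients fully followed, the standard error at month 18 is √(0.25 × 0.75 / 50) = 6.1 points, about twice the largest 18-month bias above. This also stands, and keeps the point minor.

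Two stronger readings are tempting. A reader might infer three different survival schedules, taking "12 Months, then Every 6 Months thereafter" in Appendix E as a rival to the 2-monthly calls in 6.4. It is a column header; the survival-status row beneath it says every 2 months and agrees with 6.4. Only 6.5 differs. A reader might also infer that the primary OS result is biased upward. The documents support the direction, since therapy can stop for progression and durable responses are expected in a minority. They do not give the hazards that would establish or size it.

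**Conclusion.** The contradiction is real, and nothing in the plan resolves it. If 6.5 governs, OS censoring depends on treatment duration and hence on progression. An upward bias beyond month 12 follows only if early stoppers have a higher later hazard. With median OS of 9 months assumed, the excess at 18 months is 0 with equal hazards, about 1 point or less without a durable group, and about 1 to 3 points with 20-40% durable responders, or less if progression is slow. It rises somewhat by month 21.

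Twelve-month survival, the 5-month lower-bound criterion and the stated power are unaffected. For a true median near 9 months, the median rule is essentially unaffected too. What is exposed is the late OS curve, sometimes the upper confidence limit, and any PD-L1 subgroup median above 12 months. The documents give no subgroup median, so that last exposure cannot be sized. Minor severity.

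**What to change.** Amend 6.5 so that all patients are followed for survival until death, withdrawal of consent or one common data cut-off, irrespective of when therapy stopped. That brings it into line with 6.4 and Appendices E and F; the 2-monthly contact interval there needs no change. In 14.3, add that patients not known to have died are censored for OS at the date last known alive or at the common cut-off, whichever is earlier.

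The cost is wording in two sections, plus survival calls that 6.4 and the appendices already schedule. Sample size, power and the decision rule stay as they are.
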